4.1 General Design

This cluster-randomized trial will be conducted with 14 Philadelphia CMHCs, 7 randomized to ATTOC and 7 to usual care (UC). Following randomization, study staff will visit sites to recruit clinic personnel and clients over a 4 to 6 week period. Those eligible will complete informed consent and HIPAA forms and a baseline assessment to establish pre-intervention levels on all measures (baseline). After 4-6 weeks, the ATTOC intervention will be implemented over 9 months, from Week 1 to Week 36 (with UC at the control sites). Two mid-intervention assessments (Weeks 12 and 24) will allow for performance feedback (see Outcomes Data) and mediational analyses. Week 36 (end-of-treatment; EOT) and 52 (3-months post-EOT) assessments will allow for evaluation of changes on outcomes between groups over time. All measures will be conducted at the respective CMHC

(or over the phone if necessary) and 7-day point prevalence smoking cessation will be verified using a breath carbon monoxide (CO) monitor (abstinence = < 8ppm; [93]). Figure 1 illustrates the study design.

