5.2 Total Number of Subjects and Sites

A total of 14 CHMC sites will be recruited for the trial. At each site, 12-30 staff and about 50 clients will be recruited (Total N: Staff = ~280; Clients = ~700). Procedures will be standardized across sites.

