7.1 Sample Size and Power Determination

For cluster-randomized designs, clinic is the unit of randomization and the unit of analysis is the individual. Power is reduced by variability among clinics, represented by the intra-class correlation (ICC), analogous to an R-squared. The size of the individual sample affects precision within clusters and certain outcomes are less susceptible to potential confounding vs. others (e.g., smoking rates vs. provider adherence) since they are more independent.

For Aim 1, the analysis will compare ATTOC to UC on weeks 36 (EOT) and 52 rates of adherence to guidelines for treating TUD. The sample size was determined by assessing the mean change in practice behavior detected in Guldish et al. [18]. Given the expectation from that trial that the UC mean level of practice will be 2.36 (SD=.87), the present sample of N=14 agencies (with 280 subjects) provides 80% power ($\alpha=.05$) to detect an effect if practice behavior increases by 0.32 (on a 5-point scale) if the ICC is 0. But if our ICC is .05, .10, or as high as .15, we have 80% power ($\alpha=.05$) to detect a difference between ATTOC and UC of 0.44, 0.54, and 0.62, respectively. If 15% of the personnel are lost-to-follow-up, we will have 80% power ($\alpha=.05$) to detect an effect if practice behavior increases by 0.34 for ICC=0, by 0.46 for ICC=.05, by 0.56 if ICC=0.10, and by 0.63 if ICC=.15. The effects of ATTOC were stronger at the 3-month follow-up (mean change of 0.51), vs. EOT [18], so the current power is adequate for both time-points. Likewise, because the client sample will be more than twice as large as the clinic staff sample, we will have greater than 80% power to detect differences using the measure of physician adherence collected from clients.

For Aim 2, the analysis will compare the rates of smoking cessation between the ATTOC intervention and UC at weeks 36 and 52. We can expect that UC cessation rate will be < 2% [18]. With 14 sites (n=700 clients, ITT), we have 80% power ($\alpha=.05$) to detect a difference between ATTOC and UC of 4% with an ICC=0. But if our ICC is .05, .10, or as high as .15, we have 80% power ($\alpha=.05$) to detect a difference between ATTOC and UC of 10%, 15%, and 19%, respectively, with 14 sites and n=700 client (ITT).

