For Aim 3, the analysis will use non-inferiority testing to compare mental health and QOL across ATTOC and UC at weeks 36 and 52. Standard statistical tests, which may yield a non-significant comparison of means or proportions, cannot be used to claim that the treatments are equal since "the absence of evidence is not evidence of absence". Among persons with SMI, the rate of psychiatric hospitalization nationally is 11.4% [114], which may represent UC (i.e., 88.6% of UC subjects will not have a hospitalization across the 52 weeks). One study found that 3.3% of clients with an SMI treated for TUD had a psychiatric hospitalization [48] or that 96.7% of clients treated for TUD did not experience a psychiatric hospitalization. We assume 14 sites (700 clients), with potential loss of 15% to follow-up, and assume approximately 90% non-hospitalization in the UC group. We will set our non-inferiority floor 20% below the US rate, which yields 80% power to detect non-inferiority if the ICC is as much as 0.15 (more power if ICC is less than 0.015).

A trial with smokers with an SMI reported baseline BASIS-R scores of 2.1 (SD=0.8) and SF-12 scores of 48.7 (SD=12.5) for the physical sub-scale and 27.8 (SD=12.9) for the mental sub-scale, which estimates UC [107]. Given the sample of 14 sites (700

clients) and potential 15% loss to follow-up, we have 80% power ($\alpha=0.05$) to detect non-inferiority if the results for the ATTOC arm differ from UC by as much as 0.19 on the BASIS-R, when ICC=0, and by 0.50 when ICC=0.15.

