The effects of the ATTOC model on client mental health functioning and QOL: We will compare treatment arms in terms of the frequency of hospitalizations (binary) and mental functioning evaluations (continuous) over 52 weeks. Again, we will use mixed models to account for clustering, while accommodating either the binary outcome with logistic regression or the continuous measures with linear regression. Equivalence uses two one-sided tests against lower and upper equivalence bounds. The null hypothesis is that the groups are not equivalent and are determined to be equivalent when the mean or proportion is significantly different from both boundaries. We will use this approach to determine whether hospitalization rates are higher (null) in the ATTOC group or equivalent, and whether mental functioning is lower in the ATTOC group (the null) or equivalent. All hypotheses will be tested at $\alpha=0.05$ (0.025 for any one sided non-inferiority test).

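### The stated 80% power for BASIS-R non-inferiority (Aim 3) holds only on normal-type quantiles; on the 12 df implied by 14 clinics, and by the Aim 1 figures, it is about 76% and 74%

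*Combined protocol and SAP*

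**What the plan says.** Section 7.1 (Aim 3) takes a BASIS-R SD of 0.8 from a trial in smokers with serious mental illness. It assumes 14 sites, 700 clients and 15% loss to follow-up, and says: "we have 80% power ($\alpha=0.05$) to detect non-inferiority" if the arms differ "by as much as 0.19 on the BASIS-R, when ICC=0, and by 0.50 when ICC=0.15". It gives no true difference, formula or degrees of freedom.

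Section 7.2.1 sets the overall level at 0.05, with "0.025 for any one sided non-inferiority test". For Aim 3 it plans mixed models without naming a reference distribution, and it also describes two one-sided tests against equivalence bounds. For Aim 1 it says that significance comes from a z-score for the treatment term.

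Section 7.1 (Aim 1) uses SD 0.87 and 280 personnel. It claims 80% power for 0.32 at ICC 0 and, at ICC .05, .10 and .15, "to detect a difference between ATTOC and UC of 0.44, 0.54, and 0.62, respectively". After 15% loss the four values are 0.34, 0.46, 0.56 and 0.63.

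Section 4.1 randomizes seven clinics to each arm. Section 5.2 says that at each site "12-30 staff and about 50 clients will be recruited".

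**The concern.** Treatment arm varies only between clinics, so the information for judging the arm effect comes from 14 clinic-level units, and about 12 df apply. Normal quantiles ignore this and make the detectable difference look smaller than it is. The Aim 1 figures appear to allow for the small number of clinics, while the Aim 3 BASIS-R figures in the same section appear not to. The clinics and the between-clinic contrast are the same for both aims, and the plan gives no reason for treating them differently.

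Aim 3 is one of three primary aims and carries the claim that ATTOC does not worsen mental health. What is at stake is either a lower chance of showing non-inferiority than stated, or a higher chance of declaring it falsely.

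**Working it through.** **Inputs**

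- Clinics: 14, seven per arm (section 4.1). Between-clinic df = 14 − 2 = 12.
- Clients: 700, or 50 per clinic (section 5.2). With 15% loss: 700 × 0.85 = 595 in all, 297.5 per arm, 42.5 per clinic.
- BASIS-R SD: 0.8 (section 7.1).
- Level: one-sided 0.025 (section 7.2.1). Power: 80%.
- True difference: 0. This is an assumption, because the plan states none.
- The stated 0.19 and 0.50 are treated as the non-inferiority margin at each ICC.

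**Standard error**

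SE = SD × √[(4/N) × (1 + (m − 1) × ICC)], with N = 595 and m = 42.5.

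- ICC 0: 0.8 × √(4/595) = 0.0656.
- ICC .15: design effect 1 + 41.5 × 0.15 = 7.225; SE = 0.0656 × √7.225 = 0.1763.

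**Reproducing the plan's Aim 3 figures**

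Normal quantiles: (1.960 + 0.842) × SE = 2.802 × SE.

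- ICC 0: 0.184 (stated 0.19).
- ICC .15: 0.494 (stated 0.50).

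The stated values follow if these are rounded up. A t on 593 df gives 0.184 and 0.495, so it fits equally well. A noncentral t on 12 df gives 0.200 and 0.538, which do not round to the stated values. A one-sided 0.05 level gives 0.163 and 0.438 (normal) or 0.173 and 0.465 (12 df), which also do not fit.

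**Same check on Aim 1** (SD 0.87; 280 personnel at 20 per clinic, or 238 at 17 per clinic after 15% loss; two-sided 0.05)

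| Loss | ICC | Stated | t, 12 df | Normal |
|---|---|---|---|---|
| none | 0 | 0.32 | 0.317 | 0.291 |
| none | .05 | 0.44 | 0.443 | 0.407 |
| none | .10 | 0.54 | 0.541 | 0.496 |
| none | .15 | 0.62 | 0.623 | 0.572 |
| 15% | 0 | 0.34 | 0.344 | 0.316 |
| 15% | .05 | 0.46 | 0.462 | 0.424 |
| 15% | .10 | 0.56 | 0.555 | 0.510 |
| 15% | .15 | 0.63 | 0.635 | 0.583 |

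All eight agree with 12 df to rounding (the last is 0.6349 before rounding). None agrees with normal quantiles.

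**Aim 3 power at the stated differences**

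Noncentrality = difference / SE: 0.19/0.0656 = 2.90 and 0.50/0.1763 = 2.84.

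| Reference for the one-sided test | Power at 0.19, ICC 0 | Power at 0.50, ICC .15 | Actual one-sided error |
|---|---|---|---|
| Normal theory throughout | 82.6% | 80.9% | 2.5% nominal |
| t on 12 df, critical value 2.179 | 75.8% | 74.0% | 2.5% |
| SE on 12 df but compared with 1.96 | 81.8% | 80.3% | 3.7% |

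The 3.7% is the probability that a t on 12 df exceeds 1.96.

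**Differences with 80% power on 12 df, one-sided 0.025**

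| ICC | Design effect | SE | Difference |
|---|---|---|---|
| 0 | 1 | 0.0656 | 0.20 |
| .05 | 3.075 | 0.1150 | 0.35 |
| .10 | 5.15 | 0.1489 | 0.45 |
| .15 | 7.225 | 0.1763 | 0.54 |

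**The case against.** The strongest reply is that the only reference distribution the plan names is a z-score. If Aim 3 follows it, the stated 80% is met (about 82% and 80%). That is correct about power, but it moves the defect: comparing a statistic that has 12 df with 1.96 gives a one-sided error of about 3.7%, against the 2.5% that section 7.2.1 sets. The z-score sentence also concerns Aim 1, the aim whose power figures fit 12 df.

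Second, section 7.1 writes alpha 0.05 beside the BASIS-R figures. Read as one-sided 0.05, power on 12 df would be 86% and 85%. But 0.19 and 0.50 would then not be the 80%-power differences, and section 7.2.1 sets 0.025 explicitly.

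Third, the exact df are open. Section 7.2 plans separate variance components for site effects within treatment, and sites are matched; either could lower the df. Adjustment for baseline BASIS-R could raise power. At ICC 0, 12 df is a conservative convention. All this stands and is why the powers should be read as approximate.

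A reader might infer that the sponsor knowingly used 12 df for Aim 1 and a different rule for Aim 3. The documents do not say so; both bases are inferred from reproducing the figures. A reader might also infer that one in four trials of any truly non-inferior ATTOC would fail. That holds only for a true difference of exactly zero and with 0.19 or 0.50 as the margin. Section 7.1 offers these as detectable differences at two ICCs and does not fix a BASIS-R margin.

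**Conclusion.** The stated 80% power and the stated one-sided 0.025 level cannot both hold with 14 clinics. On 12 df, power for the BASIS-R non-inferiority test is about 76% at 0.19 (ICC 0) and 74% at 0.50 (ICC .15). Equivalently, the 80%-power differences are about 0.20 and 0.54. The shortfall is modest: 4 to 6 points of power, or 0.01 and 0.04 on a score with SD 0.8. The ICC matters far more, since it alone moves the plan's own figure from 0.19 to 0.50.

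The result rests on zero true difference, equal clinic sizes, 15% loss, 12 df, and a decision by the one-sided non-inferiority test. If the two one-sided equivalence tests in section 7.2.1 were the decision rule, at 0.025 each on 12 df, power at the stated differences would be only about 52% and 49%, and 0.20 and 0.54 would not suffice.

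The finding concerns the BASIS-R figures only. It does not show that the trial is too small or that the Aim 1 figures are wrong.

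**What to change.** - **Section 7.1, Aim 3.** Restate the BASIS-R figures for a one-sided 0.025 non-inferiority test with zero true difference on 12 df: 80% power at about 0.20, 0.35, 0.45 and 0.54 for ICC 0, .05, .10 and .15. Alternatively, keep 0.19 and 0.50 and give power of about 76% and 74%. State the df, and that the Aim 1 figures are on the same basis.
- **Section 7.2.1, reference distribution.** Test the arm effect against a t with between-clinic df in place of a z-score.
- **Section 7.2.1, decision rule.** State that the Aim 3 decision rests on the one-sided non-inferiority test. If two one-sided equivalence tests are kept as the decision rule, recompute the section 7.1 figures; they will be less favourable.

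This takes a few sentences and no change in enrolment. The only cost is slightly less favourable stated figures.

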7.2 Statistical Methods

We will assess sample characteristics by treatment arm and site with chi-square or regression. These variables will also be examined for their relationship to completion of outcomes. Variables related to treatment arm or completion of follow-ups ($p < .10$) may be covariates in analyses. Fidelity and adherence measures will be evaluated across treatment arms, and the measures can be included in primary analyses. We will examine if the rate of missing data is related to a range of variables using chi-square and regression and use appropriate methods for dealing with missing data (e.g., [115]). Analyses will assume that all subjects for whom smoking outcome data are unavailable are smokers (ITT) but we can also conduct a "completers-only" analysis. Because this is a cluster-randomized trial, the observations within a cluster cannot be considered totally independent. Variation among clusters may be confounded with treatment because clusters are nested within treatment. We will account for this clustering using hierarchical linear models (mixed models), estimating separate variance components for random site effects within treatment. Lastly, since we cannot guarantee that clinicians will be blind to their clients enrolling in this study, we will include a statement in personnel consent forms asking that they refrain from asking their clients if they are enrolled in the study.

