
Statistical Methodology
	
 • Sample characteristics will be assessed by treatment arm and site with chi-square or regression for their relationship to completion of outcomes (variables related to treatment arm or completion of follow-ups may be covariates in analyses.) • Fidelity and adherence measures will be evaluated across treatment arms, and the measures can be included in primary analyses. • Rate of missing data will be assessed as related to a range of variables using chi-square and regression and using appropriate methods for dealing with missing data.

Data and Safety Monitoring Plan
	
The study will be monitored by the PIs and co-investigators, and regulatory committees at the University of Pennsylvania (i.e., IRBs, OHR) as well as by a study specific Community Advisory Council and the Philadelphia Department of Public Health Institutional Review Board. During the course of the study, safety and data quality monitoring will be performed on an ongoing basis by the Principal Investigators and the study staff.

2 Introduction

The information that follows constitutes the research protocol for the Testing an Organizational Change Model to Address Smoking in Mental Healthcare study. This study will be conducted in compliance with the provisions set forth in this document. This study will also be conducted in full accordance with all applicable University of Pennsylvania Research Policies and Procedures, Good Clinical Practice Standards and all applicable Federal and state laws and regulations including 45 CFR 46, 21 CFR Parts 50, 54, 56. All episodes of noncompliance will be documented.

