7.2.1 Analysis of Outcomes of Interest

The effects of the ATTOC model on provider adherence to guidelines for treating TUD: We hypothesize that the ATTOC intervention will increase adherence to guidelines for treating TUD vs. UC. The outcome is continuous and the hypothesis will be tested by a treatment arm term in a mixed-models linear regression model that may include covariates. Mixed models may account for individual level clustering inherent in longitudinal studies and site level clustering. Outcomes of the analysis will be characterized by regression coefficients and confidence intervals. Significance will be determined from a z-score corresponding to the treatment variable. Although level of adherence at 36 and 52 weeks will represent our primary outcome variables, similar regression analyses will be performed for assessments at Weeks 12 and 24. Also, we can examine models of specific clinician practices (e.g., identifying smoking, recommending pharmacotherapy) and examine adherence from the client perspective and based on adherence data ascertained from the EHR.

The effects of the ATTOC model on client smoking: The hypothesized effect of treatment arm (i.e., the difference in quit rates between subjects receiving the ATTOC intervention or UC) will be tested by a treatment arm term in a mixed-models logistic regression model with covariates. Outcomes of the analyses will be characterized by odds ratios (e.g., odds of quitting smoking) and 95% confidence intervals. Although quit-rates at the end of 36 and 52 weeks will represent our primary outcomes, similar analyses will be performed for other assessments of quit rates (e.g., at Weeks 12 and 24). In addition, as many participants will fail to become abstinent, we will explore the use of zero-truncated negative binomial regression for count data to examine the main effects of treatment arm on changes in smoking rate at all assessment time-points.

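### Covariates are picked by a p < .10 screen against treatment arm, and no primary model commits to the baseline value of its outcome or to the matching factors.

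*Combined protocol and SAP*

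**What the plan says.** Section 7.2 sets up a screen: "We will assess sample characteristics by treatment arm and site with chi-square or regression". The rule that follows is: "Variables related to treatment arm or completion of follow-ups ($p < .10$) may be covariates in analyses". The Statistical Methodology row of the Study Summary repeats it without the threshold: "variables related to treatment arm or completion of follow-ups may be covariates in analyses".

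Section 7.2.1 names no covariate for any primary model. For Aim 1 it describes a "mixed-models linear regression model that may include covariates". The Aim 2 logistic model is to have covariates, but they are not listed. The Aim 3 paragraph mentions none.

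Clinic effects are specified for the analysis models: "We will account for this clustering using hierarchical linear models (mixed models), estimating separate variance components for random site effects within treatment". Nothing says that the baseline screen also allows for clinic.

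Four other places bear on the point. Section 4.7 and the schedule in section 6 have a covariates heading (demographics, smoking history, FTND, psychiatric history, Dashboard). Section 6.1.1 says that baseline differences across usual-care sites can be controlled for. Section 4.2 matches clinics on size and on the ORIC score. The schedule collects S-KAP, BASIS-R and SF-12 at baseline.

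**The concern.** A covariate earns its place in a randomised comparison by predicting the outcome. Imbalance between randomised arms is a chance event and says nothing about prognosis, so screening on it selects on the wrong property. The baseline value of a continuous outcome is usually the strongest predictor available, yet here it is assured of a place in no model.

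Two features make matters worse. A plain chi-square or individual-level regression ignores the correlation within clinics, so its p-values against a clinic-level arm are too small. And because the rule is permissive, the final covariate set can be settled after outcome data are seen.

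At stake are precision in a trial of only 14 clinics and a primary analysis fixed in advance.

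**Working it through.** **Inputs from the documents.** 14 clinics, 7 per arm (section 4.1). About 280 staff and 700 clients (section 5.2), so m = 280/14 = 20 staff and 700/14 = 50 clients per clinic. Aim 1 SD .87, alpha .05 and 80% power, with ICCs of 0 and then "But if our ICC is .05, .10, or as high as .15, we have 80% power" (section 7.1).

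**Assumptions.** Alpha is two-sided. Baseline variables share the outcome ICCs. The baseline-to-outcome correlation r is not given; .3 and .5 are used, with .7 as an upper case, taken as equal within and between clinics.

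**1. Reproduce the plan's Aim 1 figures.** With design effect DE = 1 + (m − 1) × ICC and 14 − 2 = 12 df:

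MDD = (t.975,12 + t.80,12) × SD × √(2 × DE / (7m))

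For m = 20, DE is 1, 1.95, 2.90 and 3.85 at ICC 0, .05, .10 and .15. The result is 0.32, 0.44, 0.54 and 0.62, matching section 7.1. The stated power therefore assumes no baseline adjustment.

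**2. How often an irrelevant variable is flagged when the screen ignores clinic.**

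P(flag) = 2 × [1 − Φ(1.645 / √DE)]

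| ICC | DE staff | flagged | DE clients | flagged |
|---|---|---|---|---|
| 0 | 1 | 10% | 1 | 10% |
| .01 | 1.19 | 13% | 1.49 | 18% |
| .05 | 1.95 | 24% | 3.45 | 38% |
| .10 | 2.90 | 33% | 5.90 | 50% |
| .15 | 3.85 | 40% | 8.35 | 57% |

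Simulation with continuous and binary variables agrees within about 1.5 points. A clinic-level test flags about 10% at every ICC.

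**3. How often the arm screen misses the baseline score.** This is one minus the flag rate. At ICC .05, .10 and .15, baseline S-KAP is missed 76%, 67% and 60% of the time (Aim 1), and a client scale 62%, 50% and 43% of the time (Aim 3). With a clinic-aware screen, both are missed about 90% of the time. Curing the over-flagging therefore makes the omission more frequent.

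**4. What fixing baseline S-KAP would gain for Aim 1.** The MDD is multiplied by √(1 − r²). Power is at the plan's own detectable differences.

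| r | √(1 − r²) | MDD at ICC .05 / .10 / .15 | Power, always adjust | Power, p < .10 rule (simulated) |
|---|---|---|---|---|
| none | 1 | 0.44 / 0.54 / 0.62 | 80% (unadjusted) | – |
| .3 | .954 | 0.42 / 0.52 / 0.59 | 83% | about 80-81% |
| .5 | .866 | 0.38 / 0.47 / 0.54 | 89% | about 82-85% |
| .7 | .714 | 0.32 / 0.39 / 0.45 | 97% | about 87-91% |

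The simulations used 1,500 runs per setting, so each simulated figure carries an error of about one percentage point.

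**5. Type I error.** With the baseline score as the only candidate, the simulated rule rejected about 4% of the time at r = .5 and 2-3% at r = .7. It was slightly conservative.

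**The case against.** The strongest reply is that the plan loses nothing it has claimed. Its stated power is reproduced without baseline adjustment, the rule did not raise type I error in simulation, and the gain from fixing the baseline score is about 3 points of power at r = .3. The wording is also permissive: section 6.1.1, the longitudinal mixed models in section 7.2.1 and the follow-up-completion route could all bring the baseline score in. All of this stands. None of it commits a primary model to anything, and the covariates heading in the schedule does not fix those variables in a model.

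Some stronger readings are tempting, but the documents do not support them:

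- *A quarter to a half of irrelevant variables will be flagged because there are only 14 clinics.* The inflation comes from cluster size and ICC, not from the number of clinics. It also needs a screen that ignores clinic. The text allows regression and does not say whether clinic enters it.
- *The baseline outcome will usually be left out.* That fits Aim 1. For the client scales it is near even at ICC .10 and false at .15. For Aim 2 it does not arise, because every client smokes at entry (section 5.3).
- *The Aim 2 model will be overloaded with covariates.* Any events-per-covariate figure needs a number of candidate variables, which the documents do not give.
- *The completion criterion is irrelevant to Aim 2.* Missing is scored as smoking, so completion is part of the scored outcome, and section 7.2 also allows a completers-only analysis.

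**Conclusion.** The point holds as one of precision and pre-specification. Screening against arm is the wrong basis for choosing covariates, and inclusion of the baseline score is not guaranteed in any primary model. For Aim 1, relative to always adjusting, the rule gives up roughly 2-3 points of power at r = .3 and about 4-7 at r = .5.

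The text of the rule and the absence of named covariates are certain. The flag rates are conditional on a screen that ignores clinic and on outcome ICCs carrying over to baseline variables. The power gains depend on the assumed r.

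A reader might infer that the rule biases the treatment comparison. The check with the baseline score as sole candidate shows no such thing. The effect of a discretionary choice among many covariates is not sized here; the wording leaves that choice open, which is reason enough to close it.

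**What to change.** Replace the p < .10 arm screen in section 7.2, and its counterpart in the Study Summary, with a fixed set used whatever the baseline p-values:

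- **Aim 1:** baseline S-KAP adherence score.
- **Aim 2:** at most two baseline smoking variables (cigarettes per day, FTND). Events are few: at 2% versus 12% quitting, the plan's ICC .05 case, 350 × .02 + 350 × .12 = 7 + 42 = 49 quitters.
- **Aim 3:** the baseline BASIS-R or SF-12 score for the outcome analysed; prior psychiatric hospitalisation for the hospitalisation outcome.
- **All aims:** the matching factors, size and ORIC, where 14 clinics and the event count allow.

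Report baseline differences by arm descriptively, without tests. Use predictors of follow-up completion in missing-data sensitivity analyses, including the Aim 2 completers-only analysis.

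The cost is SAP wording only, since every variable is already collected. The matching factors, if included, use one or two of the 12 clinic-level degrees of freedom. The team also gives up the option of adding covariates to the primary models after seeing the data.
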